11.0 Measurement of Effect?

11.1 Primary means of assessment

Patient reported outcome data, as illustrated in the appendices will be the primary means of assessment.

11.2 Adverse Event Assessment

Adverse events will be evaluated by using CTCAE criteria based on patient reporting and nurse observation and/or assessment.

11.3 mRNA

mRNA results will be correlated with outcomes. See [Section 14.0](#).

11.4 Functional MRIs (fMRI)

fMRI results will be correlated with outcomes. See [Appendix XV](#).

12.0 Descriptive Factors

12.1 Age (*years*): <70 vs. ≥70

12.2 Duration of pain or neuropathy symptoms in months at baseline: 3 to 6 vs. >6.

13.0 Treatment/Follow-up Decision at Evaluation of Patient

13.1 Ineligible

A patient is deemed *ineligible* if after registration, it is determined that at the time of registration, the patient did not satisfy each and every eligibility criteria for study entry.

- If the patient received treatment, all data up until the point of confirmation of ineligibility must be submitted.
- If the patient never received treatment, on-study material must be submitted.

13.2 Major violation

A patient is deemed a *major violation*, if protocol requirements regarding treatment in Cycle 1 of the initial therapy are severely violated that evaluability for primary end point is questionable. All data up until the point of confirmation of a major violation must be submitted.

13.3 Cancel

A patient is deemed a *cancel* if he/she is removed from the study for any reason before any study treatment is given.

14.0 Body Fluid Biospecimens

In a subset of patients, blood will be obtained to look at mRNA gene expression in patients before and after Scrambler and TENS therapy

14.1 Summary Table of Research Blood and Body Fluid Specimens to be Collected for this Protocol*

Correlative Study (Section for more information)	Mandatory or Optional	Blood or Body Fluid being Collected	Type of Collection Tube (color of tube top)	Volume to collect per tube (# of tubes to be collected)	Baseline Prior to Tx	Last Day of Tx ± 2 days	Process at site? (Yes or No)	Temperature Conditions for Storage /Shipping
mRNA gene expression (Section 14.2)	Optional	Whole Blood	EDTA (lavender)	6 mL (1)	X	X	No	Ambient
CBC with differential for correlation with mRNA	Optional	Whole Blood	EDTA (lavender)	3 mL (1)	X	X	Yes**	Ambient

*NOTE: Collection is only at Mayo Clinic in Rochester, MN

**Process through clinical lab so results are in medical record

14.2 Collection and Processing

14.21 mRNA gene expression

The samples will be obtained prior to the first Scrambler therapy and on the last day (± 2 days) of Scrambler therapy.

14.3 Shipping and Handling

14.31 Kits will not be used.

14.32 After collection, blood will be taken directly to [name] laboratory on Guggenheim 13 for processing.

14.4 Background and Methodology

14.41 mRNA Gene Expression

We, through [name] lab, will obtain RNA expression levels that will be directly comparable to the originally reported assay, i.e., relative changes such as before and after treatment. This result will be expressed as a "fold change", such as saying "after scrambler the expression levels of gene X was increased 2-fold and Y was diminished to 0.7-fold." That calculation will be made relative to a reference gene that is assumed to be stable.

We will do RNA quantification genome-wide. The panel will then represented by genes of interest and a dozen reference genes, out of ca. 11,000-15,000 genes for which reliable expression levels will be available.

Via this process, we will look at all of the interesting-appearing genes from the Starkweather et al manuscript. This method will allow us to, hopefully, confirm that the gene changes were in line with that previously reported.

15.0 Drug Information – Not applicable**16.0 Statistical Considerations and Methodology****16.1 Primary Endpoint**

The primary endpoint of this study is the proportion of patients who achieve at least 50% reduction in pain or tingling scores from baseline after two weeks of therapy.

16.2 Study Design

This is a prospective randomized study to explore the efficacy of Scrambler therapy compared to TENS therapy for the treatment of chemotherapy induced peripheral neuropathy. Patients will be randomized at a 1:1 ratio to receive either scrambler therapy or TENS therapy for two weeks and will be observed for eight weeks following treatment. The primary outcome is the reduction in pain or tingling scores after 2 weeks of scrambler therapy or TENS therapy.

At the end of the eight-week observational period, patients are allowed to cross over to receive the other therapy for two weeks and will, again, be followed for an additional eight weeks. Outcomes of this second period of treatment are for exploratory purposes only. There will be no fMRI, quantitative sensory testing, or mRNA gene expression done in this second period.

16.3 Analysis Plan**16.31 Primary endpoint**

Evaluate the efficacy of Scrambler therapy compared to TENS therapy for pain and/or tingling related to CIPN.

The main efficacy endpoint is defined as achieving 50% reduction in pain or tingling from baseline. At enrollment, patients will be asked to select either pain or tingling as their primary symptom of concern. Allowing the patients to select their main symptom (pain or tingling) is reasonable since the scores and the patterns of reduction were similar for pain and tingling after Scrambler therapy as shown by Pachman et al. (Pachman, Weisbrod et al. 2014)

Descriptive statistics (mean, sd, median, range) of pain and tingling scores and changes pre- and post-treatment scores will be summarized and the percentage of pain and tingling reduction from baseline will be calculated for each timepoint, separately by treatment arm. Longitudinal plots of scores by arm will be provided. The frequency and percentages of patients who achieved more than 50% reduction in pain and/or tingling scores after 2 weeks of therapy (scores from the last treatment day compared to the pre-treatment data, using the question related to average symptom [pain or tingling, whichever the patient chose when entering the study] over the previous 24 hours) and after 8 weeks of observation (scores from Week 8 form) from baseline (scores from Day 1 pre-treatment form) will be summarized by treatment arm and will be compared between arms using a Chi-square test (or Fisher-exact test as appropriate).

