4.0 Test Schedule

Use for first treatment period; repeat for second treatment period

Tests and procedures	Active Monitoring Phase				
	≤30 days prior to registration	Day 1, Prior to therapy	Daily for 14 consecutive days beginning on Day 1 of active therapy	Last day of assigned therapy (±1 day)	Weekly for 8 weeks
History and exam, PS ¹ , Eligibility questions ² (Appendix II: A or B)	X				
Pregnancy test ³		X			
Declaration of most problematic site (upper versus lower extremities) and most problematic symptom (tingling versus pain): Appendix III	X				
Pain/tingling questionnaire regarding the prior week (Appendix IV: A or B)		X ⁴			
Patient Questionnaire: Before each treatment (Appendix V: A or B)		X ⁵	X ⁵		
Patient Questionnaire: After each treatment (Appendix VI: A or B)			X ⁵		
EORTC CIPN 20 (Appendix VII)		X		X ⁶	X
Patient Questionnaire: Analgesic Use (Appendix VIII)		X	X		X
Patient Questionnaire After each therapy and during weekly follow-up: Global Impression of Change and Patient Preference (Appendix IX: A or B)			X ⁷		X ⁷
Daily Treatment Log and Adverse Assessment (Appendix X)			X		
Individual Patient Dermatome Map-Electrode Placement (Appendix XI) Scrambler only			X		
Audiovisual recordings ^R			X ⁸		
Weekly follow-up patient questionnaire (Appendix XII:A or B)					X ⁹
Written patient summary (if the patient is willing to provide) ^R					X ¹⁰
Research Blood draw for CBC/diff and mRNA ^{11,R}		X		X	
fMRI ^{12,R}		X		X	
Quantitative Sensory Testing ^{13,R}		X		X	

Tests and procedures	Active Monitoring Phase				
	≤30 days prior to registration	Day 1, Prior to therapy	Daily for 14 consecutive days beginning on Day 1 of active therapy	Last day of assigned therapy (±1 day)	Weekly for 8 weeks
Study Coordinator/Nurse phone call to discuss therapy and any concerns, record any adverse events that are reported and to remind the patient to complete questionnaires and mail them			X ¹⁴		X

Footnotes:

1. PS must be done ≤7 days prior to registration.
 2. Appendix II A or B, as labeled depending on neuropathy area type. (This evaluation is used for eligibility.)
 3. For women of childbearing potential only. Must be done prior to first Scrambler therapy (or the first day of the second treatment period, if Scrambler therapy is crossover).
NOTE: This testing is not needed for TENS therapy.
 4. Appendix IV A or B, as labeled depending on neuropathy area to be treated

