7.12 Subsequent days of Scrambler Therapy

7.121 Treatment will be administered using the above outlined principles of the recommended scrambler for 30 minutes of application time, on up to 10 consecutive weekdays as long as the patient has numbness/pain/tingling rating of more than 0 at the time they come in for treatment. This is

because without pain, there is no guidance to the provider about electrode placement. Subsequent treatments can rapidly be titrated up to the highest intensity tolerated during the previous treatment. Up to three days may be skipped to allow for weekends and holidays, if needed. Treatment must start on a Monday, Tuesday, or Wednesday; with the goal being 3 consecutive days of treatment before break (e.g. treatment cannot start Wednesday before Thanksgiving holiday weekend). The total of 10 treatments must be scheduled to be able to be completed within 16 calendar days).

- 7.122 The electrode placement may be modified on subsequent days, depending on how a patient responds to treatment.

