7.2 Treatment Schedule for TENS arm

7.21 TENS Treatment Procedure

- 7.211 The patient will be given a new TENS machine that they will be able to keep. This unit will include a set of directions for use of this machine.
- 7.212 The study nurse will explain how to use the TENS machine, including a hands on learning session.
- 7.213 Written instructions will also be provided to the patient (Appendix XIV)
- 7.214 The patient will be instructed to use the TENS machine for 30 minutes per day, for 14 days, to address the area deemed most problematic (upper or lower extremities) of CIPN.
- 7.215 If the patient has questions during their 2 week treatment, they can call the study nurse.
- 7.216 The patient may also use the TENS on other areas of involvement (e.g. if their lower extremities are the main focus of the study, they may also treat their upper extremities).

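### Section 16.31 reads the two-week primary endpoint on the last treatment day: Day 14 for TENS, but Day 12, 14, 15 or 16 for a full Scrambler course and possibly earlier

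*Combined protocol and SAP*

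**What the plan says.** Section 16.1 defines response as "at least 50% reduction in pain or tingling scores from baseline after two weeks of therapy". Section 16.2 agrees: "The primary outcome is the reduction in pain or tingling scores after 2 weeks of scrambler therapy or TENS therapy". Section 16.31 is the only place that turns this into a data point: "scores from the last treatment day compared to the pre-treatment data, using the question related to average symptom", for the symptom the patient declared at entry and with the Day 1 pre-treatment form as baseline.

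The treatment schedules differ by arm:

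- **TENS (7.214):** "use the TENS machine for 30 minutes per day, for 14 days".
- **Scrambler (7.121):** "on up to 10 consecutive weekdays as long as the patient has numbness/pain/tingling rating of more than 0" on arrival, with a Monday, Tuesday or Wednesday start. "Up to three days may be skipped to allow for weekends and holidays, if needed". "The total of 10 treatments must be scheduled to be able to be completed within 16 calendar days".

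The pre-treatment questionnaire (Appendix V), which carries the 24-hour average items, sits in the Test Schedule column "Daily for 14 consecutive days beginning on Day 1 of active therapy". Footnote 5 requires it on days without therapy too. A separate column covers the last day of assigned therapy, and footnote 6 ties the CIPN-20 in that column to the time before the last session. Section 16.6 plans last value carried forward for the 14-day daily data.

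**The concern.** A primary endpoint that compares two arms should be read at the same time from baseline in both, on a day that does not depend on how the patient is doing. Taken literally, Section 16.31 secures neither.

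- **Different days.** TENS is read on Day 14; a full Scrambler course is read on Day 12, 14, 15 or 16.
- **No scheduled form.** A course that ends on Day 15 or 16 ends after the last scheduled Appendix V. The weekly form (Appendix XII) also asks the 24-hour average, but Section 16.31 does not name it for the two-week reading.
- **Possible dependence on response, in one arm only.** Section 7.121 does not say whether a zero rating skips one session or ends the course. If treatment does not resume, a patient who has become symptom-free could be scored from an earlier, symptomatic day, and a relapse before Day 14 would be missed. These two errors run in opposite directions, so no net direction can be claimed.

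The trial is described as non-confirmatory. Even so, Section 16.5 commits to treating p<0.05 on this endpoint as evidence that one therapy is better.

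**Working it through.** **1. Last treatment day.** Inputs are from Sections 7.121 and 7.214: ten weekday sessions, Monday to Wednesday start, three consecutive treatment days before the first break, no break longer than three days, and last session by Day 16. The three-day skip allowance is read per break. As a total it would allow only 10 + 3 = 13 days and would exclude ordinary Tuesday and Wednesday courses. All placements of missed weekdays were listed.

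| Weekdays missed | Monday start | Tuesday start | Wednesday start |
|---|---|---|---|
| 0 | Day 12 | Day 14 | Day 14 |
| 1 | Day 15 | Day 15 | Day 15 |
| 2 | Day 16 | Day 16 | Day 16 |
| 3 | none fits | none fits | none fits |

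For example, a Monday start with none missed treats on Days 1–5 and 8–12. The plan's 16-day limit is therefore consistent with up to two missed weekdays. Day 13 never occurs. TENS, used daily from Day 1, ends on Day 14.

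**2. Sessions completed before a Day 14 form.**

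| Weekdays missed | Monday start | Tuesday start | Wednesday start |
|---|---|---|---|
| 0 | 10 | 9 | 9 |
| 1 | 9 | 8–9 | 8–9 |
| 2 | 8–9 | 7–8 | 7–9 |

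A pre-treatment form on the day of the tenth session follows 9 sessions.

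**3. How the reading day can change a classification.** This is a hypothetical patient, assuming no treatment after a zero. The 24-hour average of the declared symptom is 4 at baseline and 3 on the Friday, the last treatment day. Numbness, pain and tingling are all 0 on arrival on Monday, and the average is 0 on Day 14.

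- Last treatment day: (4 − 3)/4 = 25% reduction, non-responder.
- Day 14: (4 − 0)/4 = 100% reduction, responder.

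**4. Sensitivity of the test.** One patient is 1/25 = 4 percentage points. The table gives two-sided p-values against TENS 5/25; the smallest expected counts are 8.0 to 9.5, so the chi-square test applies.

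| Scrambler responders | Chi-square (uncorrected) | Fisher |
|---|---|---|
| 14/25 | 0.009 | 0.019 |
| 13/25 | 0.018 | 0.038 |
| 12/25 | 0.037 | 0.072 |
| 11/25 | 0.069 | 0.128 |

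The .20 versus .54 row of Table 16.51 implies 0.54 × 25 = 13.5 Scrambler responders. From 13, losing two takes the chi-square p above 0.05; from 14, it takes three.

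The other rows, as TENS versus Scrambler responders of 25 and the number of Scrambler responders lost before p reaches 0.05:

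- .10/.40: 2 v 10 needs 3; 3 v 10 needs 2.
- .30/.65: 7 v 16 needs 3; 7 v 17 needs 4; 8 v 16 needs 2; 8 v 17 needs 3.
- .40/.75: 10 v 18 needs 2; 10 v 19 needs 3.

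The .05/.32 row is omitted because its expected counts mostly fall below 5. Any reclassification at this sample size has the same effect. These figures show sensitivity and do not estimate how many patients would be affected.

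**The case against.** The strongest reply is that the last-treatment-day phrase is only a gloss on two weeks of therapy. Sections 16.1 and 16.2 say two weeks, the Schema describes therapy as daily for 14 days, footnote 5 collects forms for 14 days with or without therapy, and Section 16.6 refers to 14-day daily data. On that reading both arms are scored on Day 14 and only the wording needs tidying. The reading is possible, but it is not secure. The Test Schedule separates the 14 daily days from the last day of assigned therapy, footnote 6 links the latter to the final session, and footnote 11 foresees earlier completion of treatment. Two analysts could extract different primary data sets.

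Three further points have force:

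- **The ordinary gap is small.** Without missed weekdays only Monday starters differ from TENS, by two days, and Section 1.4 reports that benefit in the pilot was largely maintained for 10 weeks. That gap alone would not justify a change.
- **Response-dependent timing is conditional.** The reason given in 7.121, that electrode placement needs pain as a guide, fits skipping one session as well as ending the course. Footnote 11 does not link early completion to a zero rating.
- **End of course is a defensible target.** A fixed Day 14 reads some Scrambler patients after their last session and others before it.

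The planned plots, the summaries at each time point and the Week 8 comparison would also make Day 14 results visible, but they do not say which day is primary. Nor does carrying values forward.

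**Conclusion.** The concern holds and should be fixed, with medium confidence. As written, the primary score falls on Day 14 for TENS as instructed and on Day 12, 14, 15 or 16 for a completed Scrambler course. Days 15 and 16 have no scheduled daily form. If a zero rating is not followed by further treatment, the Scrambler reading can come before Day 12 and its timing then depends on the outcome.

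This rests on the literal reading of Section 16.31, the skip allowance read per break, and TENS used as instructed. The frequency and direction of any bias are unknown. Timing alone, in full courses without missed weekdays, is a minor matter. What carries the point is the ambiguity in the primary time point, the mismatch of the 14-day and 16-day windows, and the possible dependence on response in one arm. The margin for error is narrow: over the .10 to .40 rows of Table 16.51, two to four fewer Scrambler responders take the result across 0.05.

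**What to change.** In Section 16.31, define the primary score in both arms as the Appendix V 24-hour average of the declared symptom on Day 14, whether or not treatment was given that day, with the Section 16.6 carry-forward rule if it is missing. Keep the last-treatment-day score as a sensitivity analysis. The 16-day treatment window in 7.121 and the 14-day questionnaire window in footnote 5 must be reconciled.

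The cost is one or two sentences. The Day 14 form is already scheduled in both arms, so no new data are needed. The downside is small: full-course Monday starters are read two days after their tenth session, and patients finishing on Day 15 or 16 are read with 7 to 9 sessions done, against 9 before a form on their last day.

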16.32 Secondary efficacy endpoints

Perceived treatment efficacy from the Subjective Global Impression of Change instrument (Appendix IXA and B) will be summarized (median and range for impression of change and frequency for preference) by arm and compared

(Wicoxon rank-sum test for impression of change and Chi-square test for preference) between treatment arms.

EORTC CIPN20 scores and changes in scores will be summarized (mean, sd, median, range) at each time point by arm and will be compared between arms using two-sample t-tests.

- 16.33 Goal: Evaluate the tolerability of Scrambler therapy and compare it to TENS therapy, in this population.

Frequency and type of toxicities occurred during therapy will be summarized by treatment arm and compared between arms using Fisher-exact test.

- 16.34 Goal: Evaluate whether Scrambler therapy, compared to TENS therapy, can decrease the use of pain medication for CIPN.

Type and frequency of analgesic used will be summarized by treatment arms and will be compared using Fisher-exact test.

- 16.35 Goal: Explore whether mRNA gene expression changes are similar to that previously reported by Starkweather et al.

In a descriptive manner, the gene expression will be compared to what was previously reported.

- 16.36 Goal: Explore whether Scrambler therapy will change fMRI.

Changes in fMRI following Scrambler therapy will be described in the subset of patients selected for this component of the study.

- 16.37 Descriptive statistics will be used for the data from Quantitative Sensory Testing.

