 5. Beginning on Day 1 of active treatment and continuing for 14 consecutive days, complete Appendix V daily pre/post therapy. If no therapy is received on a day during this timeframe, complete once daily. To be filled out only for primarily treated area. For post-therapy questionnaires VIA and VIB.
 6. Prior to the last therapy.
 7. Appendix IX A or B, as labeled depending on pain or neuropathy area to be treated.
 8. If patient provides written consent for AV recording. Recording may be done on any day.
 9. Appendix XII A or B, as labeled depending on pain or neuropathy area to be treated.
 10. To be completed any time after completion of active treatment.
 11. Optional use in selected patients: Blood draws are completed at Baseline (prior to treatment) and on the last planned day or two of treatment (e.g., Day 9 or 10, if 10 treatments are given but sooner if earlier treatment completion is planned) (±2 days). Ideally, do prior to treatment. See [Section 14.0](#).
 12. fMRI: Optional use in selected patients, do at baseline and on approximately the last day of the initial treatment (±1 day).
 13. Quantitative sensory testing: Optional use in selected patients, do at baseline and then the last day of the initial treatment (±3 days) on 10 patients from each cohort. Do prior to treatment.
 14. For TENS patients only: Study Coordinator or Nurse to call on Treatment Day 2 and once on Treatment Day 8-10 to assess toxicities and remind the patient to complete daily questionnaires and mail them back.
- R Research funded

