Appendix VII EORTC QLQ CIPN-20 Instrument

EORTC QLQ – CIPN20

Patients sometimes report that they have the following symptoms or problems. Please indicate the extent to which you have experienced these symptoms or problems during the past week. Please answer by circling the number that best applies to you.

During the past week:

	Not at All	A Little	Quite a Bit	Very Much
31 Did you have tingling fingers or hands?	1	2	3	4
32 Did you have tingling toes or feet?	1	2	3	4
33 Did you have numbness in your fingers or hands?	1	2	3	4
34 Did you have numbness in your toes or feet?	1	2	3	4
35 Did you have shooting or burning pain in your fingers or hands?	1	2	3	4
36 Did you have shooting or burning pain in your toes or feet?	1	2	3	4
37 Did you have cramps in your hands?	1	2	3	4
38 Did you have cramps in your feet?	1	2	3	4
39 Did you have problems standing or walking because of difficulty feeling the ground under your feet?	1	2	3	4
40 Did you have difficulty distinguishing between hot and cold water?	1	2	3	4
41 Did you have a problem holding a pen, which made writing more difficult?	1	2	3	4
42 Did you have difficulty manipulating small objects with your fingers (for example, fastening small buttons)?	1	2	3	4
43 Did you have difficulty opening a jar or bottle because of weakness in your hands?	1	2	3	4
44 Did you have difficulty walking because your feet dropped downwards?	1	2	3	4

Please go on to the next page

During the past week:

	Not at All	A Little	Quite a Bit	Very Much
45 Did you have difficulty climbing stairs or getting up out of a chair because of weakness in your legs?	1	2	3	4
46 Were you dizzy when standing up from a sitting or lying position?	1	2	3	4
47 Did you have blurred vision?	1	2	3	4
48 Did you have difficulty hearing?	1	2	3	4

Please answer the following question only if you drive a car

49 Did you have difficulty using the pedals?	1	2	3	4
--	---	---	---	---

Please answer the following question only if you are a man

50 Did you have difficulty getting or maintaining an erection?	1	2	3	4
--	---	---	---	---

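### CIPN20 is tested by unadjusted t-tests on two scales with no lead test or time point; one baseline-adjusted analysis would be a low-cost precision gain, not the repair of an error

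*Combined protocol and SAP*

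**What the plan says.** Section 16.32 (Secondary efficacy endpoints) states that "EORTC CIPN20 scores and changes in scores will be summarized" by mean, SD, median and range "at each time point by arm and will be compared between arms using two-sample t-tests". Two quantities are therefore tested, the score and its change. Neither is named as the lead, no time point is singled out, and no covariate appears.

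The Test Schedule (Section 4.0) marks CIPN20 on Day 1 before therapy, on the last day of assigned therapy and weekly for 8 weeks. A baseline is therefore in hand, with 1 + 8 = 9 later assessments in the first treatment period. Footnote 6 places the end-of-therapy form "Prior to the last therapy".

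For the primary responder endpoint, Section 16.31 says that the arms' frequencies and percentages "will be compared between arms using a Chi-square test (or Fisher-exact test as appropriate"). Section 16.3 commits to no between-arm difference with an interval for either endpoint. Section 16.5 describes the study as non-confirmatory, with estimation of the Scrambler effect as its primary purpose, at 25 patients per arm.

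**The concern.** The score test ignores where a patient started. The change test assumes that each extra point at baseline carries over as exactly one extra point at follow-up. ANCOVA estimates that slope from the data for one degree of freedom and usually gives a narrower interval. With N set mostly by feasibility, the analysis is the cheapest remaining source of precision.

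There is also a question of clarity. Two scales at up to nine times can give different answers, and the plan does not say which one will be reported as the CIPN20 result. In a study whose stated product is an estimate, one would expect one named between-arm difference with its interval.

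**Working it through.** **The plan's own figure.** The only power figures are in Table 16.51, for the responder endpoint. I used the pooled normal approximation, one-sided .05, n = 25 per arm:

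power = Φ{[d − 1.645·√(2p̄(1−p̄)/25)] / √[(p₁(1−p₁)+p₂(1−p₂))/25]}

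For .20 vs .54 this is (.34 − 1.645×.1366)/.1278 = .90, so power is 81.7%. The five rows give 80.7, 80.4, 81.7, 81.3 and 82.1% against the stated 80, 80, 81, 81 and 82%. The table reproduces and is not in question. Nothing comparable is stated for CIPN20.

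**Inputs for CIPN20.** n = 25 per arm (Section 16.5), all assumed complete. The baseline-to-follow-up correlation r and the SDs are not in the documents and are assumed. Baseline SD is set to 1 and follow-up SD to k.

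**Variance per patient**
- Score: k²
- Change: k² + 1 − 2rk
- ANCOVA: k²(1 − r²)(1 + 1/46), where 1/46 = 1/(50 − 4) is the cost of chance baseline imbalance

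The 95% half-width is t·√(2/25 × variance), with t = 2.0106 (48 df) for the t-tests and 2.0117 (47 df) for ANCOVA.

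**Equal SDs (k = 1)**

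| r | Score | Change | ANCOVA | Narrower than score | Narrower than change | Narrower than the better |
|---|---|---|---|---|---|---|
| .3 | .569 | .673 | .549 | 4% | 18% | 4% |
| .5 | .569 | .569 | .498 | 12% | 12% | 12% |
| .7 | .569 | .441 | .411 | 28% | 7% | 7% |
| .9 | .569 | .254 | .251 | 56% | 1% | 1% |

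Example at r = .5: 2.0117 × √(.08 × .75 × 1.0217) = .498, and .498/.569 = .876.

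**Unequal SDs, against the better planned test**

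| k | r = .5 | r = .7 |
|---|---|---|
| 0.8 | 12% narrower | 20% narrower |
| 1.3 | 3% narrower | 0.7% wider |
| 1.5 | 0.7% narrower | 1.0% wider |

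**Where ANCOVA loses.** There are two regions. At r = 0 it is 1.1% wider than the score test; with equal SDs it breaks even near r = .15. When the true slope rk is near 1, the change test already uses the right slope: k = 1.3 with r = .7 gives rk = .91. With equal SDs this begins at (1 + r) × 1.0217 × (2.0117/2.0106)² = 2, so r ≈ .955. At a slope of exactly 1 the loss is √1.0217 × 2.0117/2.0106 − 1 = 1.1%.

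**Can the two planned tests disagree?** Simulation with 25 per arm, equal SDs and two-sided .05: at an assumed 0.6 SD effect, one is significant and the other not in 32/33/38/45% of trials (r = .3/.5/.7/.9). At 0.3 SD it is 18/21/28/55%. With no effect, each test alone rejects in about 5%, and at least one of the two in 9–10%.

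**Interval for the responder endpoint.** Take 5 vs 14 responders of 25. The Wilson limits are .089 to .391 and .371 to .733. The Newcombe limits are .36 − √(.189² + .191²) = .09 and .36 + √(.173² + .111²) = .57, so the difference is 36 points (9 to 57). Whole counts near the table's rates give widths of 41 to 49 points.

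**The case against.** The strongest reply is that nothing here is wrong. Both t-tests are valid, CIPN20 is secondary in a study described as non-confirmatory, and no decision rule uses its p-value. That stands, and it fixes the size of the point.

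A reader might infer from the 28% and 56% figures that the plan wastes a large share of its information. It does not follow: those compare ANCOVA with the weaker planned test, and the fair comparison is with the better one. What remains is that the plan does not say which test leads, and the better one cannot be known beforehand.

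A reader might also infer that ANCOVA always wins unless baseline is uncorrelated with follow-up. It can also lose slightly when the slope is near 1. The documents give neither SD nor correlation, so the size of the gain is uncertain. Its worst case is not: about 1%.

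A third tempting reading is that 2 × 9 = 18 tests put the trial's conclusions at risk of a false positive. The text does not settle whether the phrase on time points governs the tests or only the summaries. No conclusion in Section 16.5 rests on CIPN20.

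Finally, the lack of a promised interval might be read as failure of the estimation purpose. Unadjusted intervals follow from the planned frequencies, means and SDs, so this is a missing reporting commitment and not lost information. The ANCOVA interval cannot be derived from those summaries.

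**Conclusion.** The point holds as a modest, low-cost improvement. Section 16.32 leaves the CIPN20 answer undefined between two scales and several time points, and leaves a collected baseline out of the model.

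With 25 complete patients per arm and equal SDs, ANCOVA narrows the interval by 4/12/7/1% against the better planned test at r = .3/.5/.7/.9. Over the SD ratios of 0.8 to 1.5 tabulated at r = .5 and .7, the result runs from 20% narrower to 1% wider. Neither bias nor inflated error in either single t-test is shown, and the primary test and sample size are unaffected. The risk-difference interval is a minor addition in line with Section 16.5.

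**What to change.** In Section 16.32, name the CIPN20 score to be used and one time point. Make the lead analysis an ANCOVA of that score on arm and Day 1 CIPN20. Report the adjusted mean difference with a 95% interval and treat the other weeks as descriptive.

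Week 8 is a reasonable choice: it is a scheduled form in both arms and Section 16.31 already uses that time. The last therapy day is harder to interpret because it can fall differently by arm. Scrambler is given "on up to 10 consecutive weekdays as long as the patient has numbness/pain/tingling rating of more than 0" (Section 7.12), whereas TENS patients are told to "use the TENS machine for 30 minutes per day, for 14 days" (Section 7.21). The form is also completed before the last therapy and asks how far patients have "experienced these symptoms or problems during the past week" (Appendix VII), whereas the primary endpoint uses a 24-hour average. If that day is preferred, the SAP should say so and note these differences.

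In Section 16.31, keep the chi-square or Fisher test and add the Scrambler-minus-TENS risk difference with a 95% interval, for example Newcombe's.

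The cost is wording only, with no new data. ANCOVA uses 1 df and assumes a linear relation to baseline. A patient without a Day 1 CIPN20 drops out, as in the planned change test. Formal comparison at the other weeks is given up.
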